7.9.6 Other Observations Related to Safety

All results for the physical examination, neurological examination, meal time, telemetry, C-SSRS, and pregnancy avoidance counseling will be presented in data listings.

The C-SSRS has 2 domains, Suicidal Ideation, and Suicidal Behavior.

Treatment-emergent suicidal ideation compared with Baseline and treatment-emergent suicidal behavior compared with Baseline will be summarized by category, visit, and TAK-653 dose level.

7.10 Interim Analysis

Not applicable.

7.11 Changes in the Statistical Analysis Plan

The analysis for EEG pharmacodynamic parameters outlined in the Section of 13.1.4 in Protocol TAK-653-1001 [1] will be performed outside this SAP.

8.0 REFERENCES

- 1. Protocol: A Phase 1, Randomized, Double-Blind, Placebo-Controlled, Safety, Tolerability and Pharmacokinetic Study of Escalating Single and Multiple Doses of TAK-653 in Healthy Subjects Amendment 6, 24 March 2017.
- 2. Brian P. Smith, etc. (2000), Confidence Interval Criteria for Assessment of Dose Proportionality, Pharmaceutical Research, Vol. 17, 10:, 1278-1283.
- 3. Hedges, L. and Olkin, I. (1985) Statistical Methods for Meta-Analysis. New York: Academic Press, Page 86.

| Appendix A | Criteria for Identification of Markedly Abnormal Laboratory Values |
|-------------|--|
| Hematology- | -Criteria for Markedly Abnormal Values |

| Parameter | Unit | Low Abnormal | High Abnormal |
|---------------------------|--------------|-------------------------------------|------------------------------------|
| Hemoglobin | Both | < 0.8 × LLN | > 1.2 × ULN |
| Hematocrit | Both | $< 0.8 \times LLN$ | $> 1.2 \times ULN$ |
| RBC count | Both | $< 0.8 \times LLN$ | $> 1.2 \times ULN$ |
| WBC count | Both | <0.5 x LLN | >1.5 x ULN |
| Platelet count | Conventional | $<75 \text{ x } 10^{3}/\mu\text{L}$ | $>600 \text{ x } 10^3/\mu\text{L}$ |
| | SI | <75 x 10 ⁹ /L | >600 x 10 ⁹ /L |
| Neutrophils (Absolute) | Both | <0.5 x LLN | >1.5 x LLN |
| Neutrophils (Relative) | Both | <0.5 x LLN | >1.5 x LLN |
| Lymphocytes (Absolute) | Both | <0.5 x LLN | >1.5 x LLN |
| Lymphocytes (Relative) | Both | <0.5 x LLN | >1.5 x LLN |
| Monocytes (Absolute) | Both | | >2 x ULN |
| Monocytes (Relative) | Both | | >2 x ULN |
| Eosinophils (Absolute) | Both | | >2 x ULN |
| Eosinophils (Relative) | Both | | >2 x ULN |
| Basophils (Absolute) | Both | | >3 x ULN |
| Basophils (Relative) | Both | | >3 x ULN |

LLN=lower limit of normal, RBC=red blood cell, ULN=upper limit of normal, WBC=white blood cell.

| Parameter | Unit | Low Abnormal | High Abnormal |
|----------------------|--------------|--------------|---------------|
| ALT | Both | | >3x ULN |
| AST | Both | | >3x ULN |
| GGT | Both | | >3x ULN |
| Alkaline phosphatase | Both | | >3x ULN |
| Calcium | Conventional | <7.0 mg/dL | >11.5 mg/dL |
| | SI | <1.75 mmol/L | >2.88 mmol/L |
| Chloride | Conventional | <75 mEq/L | >126 mEq/L |
| | SI | <75 mmol/L | >126 mmol/L |
| Total bilirubin | Conventional | | >2.0 mg/dL |
| | SI | | >34.2 μmol/L |
| Direct bilirubin | Both | | >2 ULN |
| Albumin | Conventional | <2.5 g/dL | |
| | SI | <25 g/L | |
| Total protein | Both | <0.8x LLN | >1.2x ULN |
| Creatinine | Conventional | | >2.0 mg/dL |
| | SI | | >177 µmol/L |
| Blood urea nitrogen | Conventional | | >30 mg/dL |
| | SI | | >10.7 mmol/L |
| Sodium | Conventional | <130 mEq/L | >150 mEq/L |
| | SI | <130 mmol/L | >150 mmol/L |
| Potassium | Conventional | <3.0 mEq/L | >6.0 mEq/L |
| | SI | <3.0 mmol/L | >6.0 mmol/L |
| | | | |
| Glucose | Conventional | < 50 mg/dL | >350 mg/dL |
| | SI | < 2.8 mmol/L | >19.4 mmol/L |
| Bicarbonate | Conventional | <8.0 mEq/L | |
| | SI | <8.0 mmol/L | |
| Creatine kinase | Both | | >5x ULN |

Serum Chemistry—Criteria for Markedly Abnormal Values

ALT=alanine aminotransferase, AST=aspartate aminotransferase, GGT=γ-glutamyl transferase, LLN=lower limit of normal, ULN=upper limit of normal.

| Parameter | Unit | Lower Criteria | Upper Criteria |
|--------------------------|-------|----------------|----------------|
| Pulse | bpm | <40 | >110 |
| Systolic blood pressure | mm Hg | <85 | >160 |
| Diastolic blood pressure | mm Hg | <45 | >100 |
| Body temperature | °C | < 35.6 | >37.7 |

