## 9.1.8 Procedures for Clinical Laboratory Samples

All samples will be collected in accordance with acceptable laboratory procedures. Laboratory samples will be taken following a minimum 10-hour overnight fast on the days stipulated in the Schedule of Study Procedures for SRD Part 1 (Appendix A and Appendix B) and SRD/MRD Part 2 (Appendix C).

Table 9.b lists the tests that will be obtained for each laboratory specimen.

**Table 9.b** Clinical Laboratory Tests

Hematology	Serum Chemistry	Urinalysis
Red blood cells (RBC)	ALT	pН
White blood cells (WBC)	Albumin	Specific gravity
with differential (absolute	Alkaline phosphatase	Protein
counts)	AST	Glucose
Hemoglobin	Total bilirubin	Blood
Hematocrit	Direct bilirubin	Nitrite
Platelets	Total protein	Leukocyte esterase
PT/INR	Creatinine	Ketones
aPTT	Blood urea nitrogen	Bilirubin
	Creatine kinase	Urobilinogen
	γ-Glutamyl transferase (GGT)	
	Potassium	
	Sodium	
	Glucose	
	Chloride	
	Bicarbonate	
	Calcium	

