#### 13.1.6.1 Clinical Laboratory Evaluation

Individual results of laboratory tests from hematology, chemistry, and urinalysis that meet Takeda's markedly abnormal value (MAV) criteria to be defined in the SAP will be listed and summarized. Baseline, postdose, and change from Baseline to postdose laboratory data will be summarized. All clinical laboratory data will be listed.

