5.0 ANALYSIS ENDPOINTS

5.1 **Primary Endpoints**

The primary endpoints will be the following safety variables:

- Percentage of subjects who experience at least 1 treatment-emergent adverse event (TEAE).
- Percentage of subjects who discontinue due to an AE.
- Percentage of subjects who meet the markedly abnormal criteria for safety laboratory tests at least once post-dose.
- Percentage of subjects who meet the markedly abnormal criteria for vital sign measurements at least once post-dose.
- Percentage of subjects who meet the markedly abnormal criteria for safety electrocardiogram (ECG) parameters at least once post-dose.
- Percentage of subjects who experience clinically significant abnormal changes in EEG measurements at least once post-dose.
- Columbia-Suicide Severity Rating Scale (C-SSRS):
 - Treatment-emergent suicidal ideation compared to Baseline, as measured by an increase in suicidal ideation category (1-5 on the C-SSRS) during treatment from the maximum suicidal ideation category at Baseline, or any suicidal ideation during treatment if there was none at Baseline.
 - Treatment-emergent suicidal behavior compared to Baseline, as measured by an increase in suicidal behavior category (6-10 on the C-SSRS) during treatment from the maximum suicidal behavior category at Baseline, or any suicidal behavior during treatment if there was none at Baseline.

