7.9 Safety Analysis

For each part, data for all subjects in the safety analyses set will be summarized by pooled placebo and each TAK-653 dose level for clinical laboratory, vital signs, ECG, and C-SSRS results, and by pooled placebo, each TAK-653 dose level, pooled TAK-653, and overall total for other safety variables. These summaries will not contain data from the food effect cohort (SRD Cohort 3); data from this cohort will be summarized separately by placebo fed, placebo fasted, TAK-653 fed, and TAK-653 fasted.

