7.9.2 Clinical Laboratory Evaluations

Clinical laboratory tests include hematology, serum chemistry and urinalysis.

Descriptive statistics (N, mean, median, SD, minimum and maximum) of clinical laboratory variables in SI units will be summarized for Baseline, postdose, and change from Baseline at each visit. Only the scheduled measurements will be included in the summary. No statistical tests will be performed.

Individual results for hematology and chemistry laboratory tests will be evaluated against the Takeda predefined laboratory markedly abnormal value (MAV) criteria (Appendix A) using the result and criteria in SI units. All subjects with results that meet the MAV criteria will be presented in a data listing. The number and percentage of subjects with at least one postdose markedly abnormal laboratory test result will also be summarized. The mapping of the subjects who meet the MAV criteria after dosing will be listed as a table. All postdose clinical laboratory results within 7 days of the last dose, including scheduled and unscheduled measurements, will be included in the MAV summaries.

All clinical laboratory data will be presented in both SI and conventional units in data listings.

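### SAP Appendix A sets the high markedly-abnormal limit for neutrophils and lymphocytes at 1.5 × LLN instead of a multiple of ULN, so normal counts are flagged whenever ULN exceeds 1.5 × LLN

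*SAP*

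**What the plan says.** The hematology table in SAP Appendix A has a low and a high criterion for each parameter. Absolute neutrophils read "Neutrophils (Absolute) | Both | <0.5 x LLN | >1.5 x LLN" and absolute lymphocytes "Lymphocytes (Absolute) | Both | <0.5 x LLN | >1.5 x LLN". The two relative rows carry the same limits. Total white cells, in the same table and with the same multipliers, read "WBC count | Both | <0.5 x LLN | >1.5 x ULN". The table's footnote defines LLN and ULN as the lower and upper limits of normal.

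The criteria are used as follows:

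- Protocol 13.1.6.1 sets no limits of its own. It refers to "markedly abnormal value (MAV) criteria to be defined in the SAP will be listed and summarized".
- SAP 7.9.2 judges hematology results against Appendix A, using all scheduled and unscheduled postdose results within 7 days of the last dose. It adds: "The number and percentage of subjects with at least one postdose markedly abnormal laboratory test result will also be summarized".
- SAP 5.1 lists as a primary endpoint: "Percentage of subjects who meet the markedly abnormal criteria for safety laboratory tests at least once post-dose".
- SAP 7.9 has the data "summarized by pooled placebo and each TAK-653 dose level for clinical laboratory, vital signs, ECG, and C-SSRS results".

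Protocol Table 9.b lists white cells "with differential (absolute" counts), so the two absolute rows certainly apply. The two relative rows may never be used.

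**The concern.** A high-side criterion should lie above the normal range. Here the unflagged band runs from 0.5 to 1.5 × LLN and is centred on the lower limit of normal, so a count well inside the normal range can be labelled markedly abnormal.

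One such count on one postdose draw makes the subject a case for the primary laboratory MAV endpoint. Healthy volunteers would be flagged at similar rates on placebo and on every dose. The percentages would be pushed towards the ceiling in all groups, and a real difference in other analytes would be hard to see. The MAV listing and subject mapping would also fill with normal neutrophil and lymphocyte results.

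**Working it through.** **Is it the odd one out?** High limits in Appendix A that are multiples of a normal limit, other than the four in question:

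- Hematology: hemoglobin, hematocrit, RBC, WBC, and monocytes, eosinophils and basophils (absolute and relative for each) = 10.
- Chemistry: ALT, AST, GGT, alkaline phosphatase, direct bilirubin, total protein, creatine kinase = 7.

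All 17 use ULN. Four identical LLN cells beside correctly printed ULN cells are unlikely to be a PDF-reading artefact.

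**When does the limit cut into the normal range?** Let R = ULN/LLN. Then 1.5 × LLN < ULN exactly when R > 1.5. The share of the reference interval above the limit is (R − 1.5)/(R − 1): 0% at R = 1.5, 50% at 2, 67% at 2.5, 75% at 3. Above R = 2 the midpoint of the normal range is itself flagged, because (1 + R)/2 > 1.5.

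**How many healthy subjects would be flagged?** The plan gives no figure to reproduce and no reference ranges (protocol 9.1.8 leaves these with the investigator). Assumptions:

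- Counts are log-normal, with LLN and ULN at the 2.5th and 97.5th percentiles.
- Only the two absolute counts are used.
- Scheduled postdose draws k: 3 in SRD (Days 2, 5, and 7 or 8; protocol Appendices A and B) and 6 in SRD/MRD (Days 6, 9, 12, 15, 18, 21; Appendix C).
- Within-subject correlation ρ is 0.5 to 0.7.

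Formulas:

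- SD of the log count: s = ln(R)/3.92.
- Cut in SD units: c = −1.96 + ln(1.5)/s as printed; c = 1.96 + ln(1.5)/s with ULN.
- One sample: P = 1 − Φ(c). At R = 2: s = 0.693/3.92 = 0.177, c = −1.96 + 0.405/0.177 = 0.33, P = 0.37.
- One count over k draws: p₁ = 1 − E[Φ((c − √ρ X)/√(1−ρ))ᵏ], with X standard normal.
- Two independent counts: 1 − (1 − p₁)². With correlation 0.5 between the counts: simulation, 400,000 subjects.

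Ranges run from k = 3, ρ = 0.7 to k = 6, ρ = 0.5:

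| R | One sample, one count | Subject, one count | Subject, two counts, correlation 0.5 | Subject, two independent counts |
|---|---|---|---|---|
| 1.5 | 2.5% | 5–10% | 10–18% | 11–20% |
| 1.75 | 19% | 33–50% | 48–68% | 55–75% |
| 2 | 37% | 55–75% | 72–88% | 80–94% |
| 2.5 | 59% | 77–91% | 90–97% | 95–99% |
| 3 | 70% | 85–95% | 95–99% | 98% or more |

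At R = 1.5 the printed limit equals ULN, so the flagged values lie above the normal range but are not markedly high.

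**Same calculation with ULN.** Two independent counts in the worst case (k = 6, ρ = 0.5): 0.01% at R = 2, 0.36% at 3, 1.7% at 5.

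**Masking.** If a share q of every group is falsely flagged, independently of other MAVs, a true difference D in those other MAVs appears as D × (1 − q). With a purely hypothetical D of 45 points (5% against 50%): 45 × 0.20 = 9 points at q = 80%, 45 × 0.06 = 2.7 at 94%, and 45 × 0.01 = 0.45 at 99%.

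**The case against.** The strongest reply is that this is an obvious slip with limited reach. The MAV tables are descriptive, and SAP 7.9.2 plans no statistical tests. The cohort stopping criteria in protocol 6.3.1 and the escalation rules in 6.1.3 do not use MAV criteria. Clinical significance is judged by the investigator, and change-from-baseline summaries and full listings remain. The required MAV listing and subject mapping would show which analyte caused each flag, so the error could be noticed and undone. All of that stands: no subject-safety decision turns on these cells. If the summary is also broken down by test, which the SAP does not say, the other analytes could still be read.

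The size also depends on an unknown ratio. Between 1.5 and 1.75 the effect is smaller, and at 1.4 the rule flags under 3% of subjects. The masking example uses invented rates. The draw counts leave out unscheduled samples and the second period of SRD Cohort 3, which is summarized separately. The replacement multiple is inferred from the WBC row; monocytes, for example, use 2 × ULN.

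None of this makes the printed limit right. The SAP is the programming specification. Followed literally, it gives a misleading primary-endpoint table at any ratio appreciably above 1.5. If programmers quietly use ULN instead, the outputs will not match the SAP.

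**Conclusion.** The four cells are wrong as written, and nothing in either document overrides them. That normal counts are flagged whenever ULN/LLN exceeds 1.5 is algebra and needs no assumption. How many subjects are affected depends on the assumed ratio and distribution. Across the three ways of treating the two counts, roughly 33–75% of healthy subjects would be flagged at a ratio of 1.75, 55–94% at 2, and 85% to nearly all at 3.

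The damage is confined to the laboratory MAV percentage, listing and mapping. Because that percentage is a stated primary endpoint, the correction should be made before the outputs are used. Low-side limits, other analytes' criteria, adverse event reporting and stopping rules are unaffected.

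**What to change.** Check the four High Abnormal cells (neutrophils and lymphocytes, absolute and relative) against the sponsor's predefined MAV standard and replace LLN with ULN. The likely value is 1.5 × ULN, matching the WBC row, but the multiple should be confirmed. State whether the two relative rows apply, given that Table 9.b specifies absolute counts. Do this before the laboratory MAV outputs are run. If they already exist, re-run the summary, listing and mapping and document the correction.

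The cost is four table cells and possibly one re-run. It needs no new data and puts no burden on subjects.

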Appendix B Criteria for Markedly Abnormal Values for Vital Signs

| Parameter | Unit | Lower Criteria | Upper Criteria |
|---------------|------|----------------|--|
| Heart Rate | bpm | < 50 | > 120 |
| PR | msec | ≤ 110 | ≥ 220 |
| RR | msec | ≤ 600 | \geq 1440 |
| QRS | msec | ≤ 75 | ≥ 110 |
| QT Interval | msec | \leq 50 | \geq 460 |
| QTcF Interval | msec | ≤ 50 | >=450 or >=30 change from Baseline or >=60 change from Baseline |

